Limitations: This study is limited to studying C3 and C4 genetic differences and their relationships to differences in complement and cardiometabolic risk factors and not social and lifestyle differences between the two racial groups. An extremely interesting finding would be racial differences in complement levels without significant difference in complement genetics. This would suggest that differences in lifestyle (physical activity, socioeconomic stress) may play a significant role in causing complement racial differences. Even if no racial differences are found, these studies will still generate important information regarding the relationship of complement to cardiometabolic risk in adolescents and will indicate what areas should be explored to gain a better understanding of the racial risk differences.

Future Directions: Correlational, cross-sectional studies do not prove causation so if these results demonstrate significant relationships between complement and/or complement genetics in cardiometabolic risk then future longitudinal follow-up studies will be important. It would also be important to extend these findings to additional ethnic groups. Examining the effects of socioeconomic and cultural differences on the relationships of complement to cardiometabolic risk factors may also be of value. Our results also have potential value to inform future treatment studies to prevent or reduce cardiometabolic risk. The most immediate would be using complement genetics to potentially identify subjects at high risk for future cardiometabolic disease. Furthermore, various anti-complement therapies are being developed for use in a variety of diseases.⁸⁶⁻⁸⁸

REFERENCES

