Our **Specific Aims** are:

1. To determine whether there are racial differences in complement C3 and C4 levels in healthy adolescents and how they relate to cardiometabolic risk factors including triglyceride and LDL levels, inflammation, and vascular function.
2. To determine whether specific C3 polymorphisms including F versus S, A>G at rs11569562 and/or rs2250656, are associated with increased cardiometabolic risk in African-Americans.
3. To determine whether C4 gene copy number variation is associated with increased cardiometabolic risk in African-American adolescents.

Both traditional and nontraditional cardiometabolic risk markers, including measures of body habitus [BMI, waist circumference, percent body fat], blood pressure, lipids [triglycerides, HDL and LDL cholesterol], endothelial function [reactive hyperemia, endothelin 1], insulin secretion and sensitivity [oral glucose tolerance test], inflammation [high sensitivity c-reactive protein (CRP), interleukin 6 (IL6)], and clotting [fibrinogen, plasminogen activator inhibitor 1 (PAI1)] will be investigated. Doing these studies in adolescents before the development of overt cardiometabolic disease or other co-morbidities and their treatments that may confound these relationships is important. ***This research will help us better understand physiological mechanisms for racial differences in cardiometabolic risk and thus allow us to develop targeted therapeutics to decrease the increased cardiometabolic risk in African-Americans.***

BACKGROUND AND SIGNIFICANCE

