Increased C4S copy number was associated with increased insulin secretion ($\beta=0.29$; CI: 0.06-0.52) and decreased endothelin 1 ($\beta=-0.15$; CI: -0.30--0.01). WBC ($\beta=-0.79$; CI: -1.56--0.02) and neutrophil count ($\beta=-0.87$; CI: -1.48--0.33) both decreased with increasing C4B copy number.

Figure 2: Relationship of HDL to C4 type copy number. C4L: $\beta=3.59$; CI: 1.19-6.00; C4S: $\beta=0.4.26$; CI: -7.50—1.02; C4A: $\beta=4.33$; CI: 1.00-7.66; C4B $\beta=-5.56$; CI: -10.3--0.87.

Interestingly, the measures of inflammation, IL6 and CRP were not related to C4 copy number nor were AIX₇₅ or PAI-1.

RESEARCH DESIGN AND METHODS

All three specific aims will be studied using the same subjects and research procedures.

Subjects: One hundred Africa-American adolescents between the ages of 12 and 18 will be recruited to participate. There will be no weight or BMI criteria and we plan to recruit subjects across a wide range of BMI's. This will allow us to determine the role of C3 and C4 levels, C3 polymorphisms and C4 copy number variation in determining adolescent obesity and cardiometabolic risk. Subjects must be on no chronic medications except for contraceptives in females. Subjects will be expected to be medication free for at least 2 weeks prior to study except for contraceptives. Subjects with a history of autoimmune disease, either endocrine or connective tissue type will be excluded. Subjects with a history of hematologic or renal disease, malignancy or other chronic disease will also be excluded. Subjects with a history of asthma or attention deficit disorder will be allowed to participate as long as they meet the medication requirements.

To avoid potential racial confounders as described in the preliminary data, we plan to recruit only African-American subjects. Subjects will be recruited to specifically fill 3 different weight classes (70 % lean, BMI <85%: 10% overweight BMI<95%: 20% obese BMI>95%) for both sexes. These match the reported US prevalences for overweight and obesity.⁷⁶

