Complement genotypes: C3 genetic variants including the DNA sequence polymorphisms for G102R for fast and slow allotypes, and SNPs for rs11569562 and rs2250656 that modulate C3 plasma protein levels will be typed for all study subjects. Copy-number variations for total C4, C4A, C4B, long genes and short genes of C4 will be elucidated by Southern blot analyses of genomic DNA samples digested by Pmel, Taql, PshAI/Pvull and resolved by gel electrophoresis.⁷⁴ Samples for subjects with ambiguous data will be subject to realtime quantitative PCR using five different amplicons and the results will be validated as the gene copy-numbers in each subject for total C4=C4A+C4B=long genes+short genes.⁸⁵

Cardiovascular measures, glucose and insulin: IL6, CRP, endothelin 1, fibrinogen, PAI1 glucose and insulin will be measured in the CORE laboratory. Plasma lipids will be measured in the clinical laboratory of the Wexner Medical Center.

Data analysis: **Specific Aim 1:** To determine whether there are racial differences in complement C3 and C4 levels in healthy adolescents and how they relate to cardiometabolic risk factors including triglyceride and LDL levels, inflammation, and vascular function.

Statistical methods: Complement levels from African-Americans in this proposal will be compared to those from nonHispanic whites in our current study. Eligibility criteria are identical for both studies except for race. Data will be assessed for normality using the Shapiro Wilk test ($p>0.05$ indicative of normality). Non-normal data will be log normalized if possible. Unpaired t-tests will be used to compare differences in C3 and C4 levels as well as cardiometabolic risk factor results (reactive hyperemia, augmentation index, Matsuda index, insulin secretion, lipids, inflammatory markers, and PAI-1). We anticipate age and BMI differences will be minimal but should racial differences be found analysis of covariance will be done to account for any difference found.

Robust rank order regression analysis will be used to assess relationships between C3 and C4 protein levels to body habitus, lipids, inflammation, carbohydrate metabolism, and clotting factor in each race individually and in the group as a whole. Age and sex will be included in all models. The cut-off point for outliers was 3 and 100 iterations were performed. Results are presented as 95% confidence intervals.

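### Contraceptives are the only medication allowed at entry, yet contraceptive status enters no Aim 1 analysis, leaving a potential confounder of unknown size unexamined

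*Combined protocol and SAP*

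**What the plan says.** Under Research Design and Methods, Subjects, the chronic-medication rule reads "Subjects must be on no chronic medications except for contraceptives in females", and the short-term rule reads "Subjects will be expected to be medication free for at least 2 weeks prior to study except for contraceptives". No other drug class is exempt: subjects with asthma or attention deficit disorder may enter only "as long as they meet the medication requirements".

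The Specific Aims section explains why adolescents are studied. It refers to a stage "before the development of overt cardiometabolic disease or other co-morbidities and their treatments that may confound these relationships is important".

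Under Data analysis, Specific Aim 1, Statistical methods, the race comparison is specified as "Unpaired t-tests will be used to compare differences in C3 and C4 levels as well as cardiometabolic risk factor results". Adjustment is conditional: "We anticipate age and BMI differences will be minimal but should racial differences be found analysis of covariance will be done". For the regressions of risk factors on C3 and C4, run in each race and in the pooled group, the plan says "Age and sex will be included in all models". The Aim 3 methods repeat that sentence, and the Aim 2 tests name no covariates.

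The Aim 1 Interpretation paragraph treats the explanatory hypothesis as shown if complement stays significant in the regression while the race difference disappears.

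Contraceptive use does not appear as a covariate, stratum, sensitivity analysis or reported characteristic. The Study Visit section provides for a medical history to confirm eligibility.

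**The concern.** The plan keeps all but one class of medication out and then does not look at that class in the analysis. Two features that might seem to cover this do not:

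- **The sex term.** It removes the average difference between males and females. It does not separate users from non-users among females. The race t-test does not adjust even for sex.
- **Identical eligibility in the two cohorts.** This equalises permission to use contraceptives, not actual use. The white subjects come from a separate study, and nothing in the plan checks whether use is balanced.

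Two Aim 1 results are exposed, under different conditions. The race contrast is biased if the share of users, the product type or the effect of use differs between cohorts. The complement-to-risk-factor regressions, and the rule that race loses its effect once complement is included, can be distorted even when use is equal in both cohorts, provided use shifts both complement and the marker. In the first case a difference in contraceptive use would be read as a racial difference. In the second, an association caused by contraceptive use would be credited to complement, or a real one hidden.

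**Working it through.** **The plan's own benchmarks**

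Aim 1, Sample size: 100 against 100, power 0.8. Two-sided alpha of 0.05 is assumed, because none is stated for this aim.

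- Detectable difference = (1.960 + 0.842) × √(2/100) = 0.396 SD (0.398 with the t distribution).
- The stated differences of 7.5% in C3 and 15% in C4 then imply coefficients of variation of 7.5/0.398 = 18.8% and 15/0.398 = 37.7%. The documents give no SD, so these figures are possible but cannot be verified.

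Aim 3, Sample size: r = 0.28 with 99 subjects. Fisher's z gives n = ((1.960 + 0.842)/atanh 0.28)² + 3 = 97.8, so 98, which agrees with the plan. It serves here only as a yardstick for a correlation.

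**Inputs for the illustration**

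- Female share: 0.5, assumed. The Preliminary Studies section gives 34/75 = 45% for the white sample; no ratio is stated for the new cohort.
- Difference between cohorts in use among females: 0 to 30 percentage points, assumed.
- Effect of use on a marker, or on complement: 0.5 to 1 SD, assumed.
- Use among females within a cohort: 20% to 40%, assumed.

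**Race contrast**

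Bias = female share × difference in use × effect of use, assuming the same effect in both cohorts.

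| Difference in use | Effect of use | Bias (SD) | Share of 0.396 SD | Type I error |
|---|---|---|---|---|
| 0 points | any | 0 | 0% | 5% |
| 10 points | 0.5 SD | 0.5 × 0.10 × 0.5 = 0.025 | 6% | 5.4% |
| 20 points | 1 SD | 0.5 × 0.20 × 1 = 0.10 | 25% | 11% |
| 30 points | 1 SD | 0.5 × 0.30 × 1 = 0.15 | 38% | 18% |

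The type I error is the rejection rate of the two-sided test with no true difference, at noncentrality bias/√(2/100). For the last row this is 0.15/0.1414 = 1.06.

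With the 45% female share, the last row becomes 0.453 × 0.30 × 1 = 0.136 SD.

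**Within-cohort regression**

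With a share u of females using, the variance of use after adjustment for sex is v = 0.5 × u(1 − u). If use shifts complement by d₁ SD and the marker by d₂ SD, the induced sex-adjusted correlation is

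r = v d₁ d₂ / √[(1 + v d₁²)(1 + v d₂²)].

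- u = 0.20, d₁ = d₂ = 0.5: v = 0.08, r = 0.02/1.02 = 0.02.
- u = 0.40, d₁ = d₂ = 1: v = 0.12, r = 0.12/1.12 = 0.11.

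Both lie well below 0.28. If use does not shift complement, d₁ = 0 and r = 0.

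**The case against.** **A contradiction of the protocol's own aim?** A reader might infer that the protocol set out to exclude this confounder and then let it in. The documents do not support that. The rationale in Specific Aims concerns "other co-morbidities and their treatments that may confound these relationships is important", that is, treatments of disease. Contraceptives are not named there, they are expressly permitted in both medication rules, and the Subjects section gives no reason for those rules. This is an unmodelled covariate, not a breach of a stated purpose.

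**No effect shown.** Nothing in the documents says that contraceptives act on lipids, insulin indices, inflammation, clotting factors or complement. The Preliminary Studies report no sex difference in C3 or C4, which is the only evidence available and does not favour a large effect on complement. It is weak, since there were 34 females, the number of users is not reported, and the statement says nothing about the risk markers. The objection stands to this extent: the confounder is potential and every effect size above is an assumption.

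**Small size.** The race bias is zero if use and effect are equal, and the induced correlations are far below 0.28. The 30-point end of the range also needs use outside 20% to 40% in at least one cohort; inside that range the maximum is 20 points, hence 0.10 SD. All of this stands. It argues for a modest check rather than a redesign. Some preliminary intervals do exclude zero only narrowly (LDL on C3, 0.0004 to 0.041), so even a small induced association could change how a result is read.

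**Reach.** A reader might extend the point to fibrinogen in the race comparison or to the genetic aims. Fibrinogen is not among the variables listed for the race t-tests. The exposures in Aims 2 and 3 are germline, which contraceptive use cannot alter, so there the issue is mainly precision.

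**Conclusion.** The point holds for Aim 1, as a low-cost improvement. The documents establish that contraceptives are the only exempt medication and that no planned analysis takes account of their use. Neither the sex term nor identical eligibility fills that gap. They do not establish that bias exists. Under the assumptions listed, the race contrast could be off by 0 to 0.15 SD against a detectable difference of about 0.40 SD, and the within-cohort correlation by about 0.02 to 0.11. The upper ends need a large imbalance in use or a full 1 SD effect. The direction of any bias cannot be predicted from the documents. Without reporting use by cohort, the sponsor cannot show that the bias is negligible, even if it is.

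**What to change.** Leave the eligibility criteria as they are and change the Aim 1 analysis only.

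1. **Code use.** Record current hormonal contraceptive use as yes or no, with non-hormonal methods coded as no. Estrogen-containing against progestin-only can be kept as an optional subtype. In the African-American cohort, take this from the medical history; in the white cohort, from existing records where available. If only any contraceptive use is recorded there, code any use yes or no in both cohorts so that the variable means the same thing.
2. **Report** use by cohort.
3. **Regressions.** Add the term beside age and sex in the Aim 1 models, including those used to judge whether the race difference disappears once complement is included.
4. **Race comparison.** As a sensitivity analysis, repeat it for complement, lipids, inflammatory markers, PAI-1 and insulin indices, once adjusted for use and once without users.

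For Aims 2 and 3 the term is optional.

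Cost: one coded variable, one degree of freedom per model and fewer subjects in the analysis without users. Visits and sample size do not change. The main practical risk is incomplete records in the white cohort, since the documents do not show that use or type was retained there. If so, that should be stated as a limitation.

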Insulin sensitivity and secretion: Subjects will be given 1.75 grams/kg of oral glucose (up to a maximum of 75 grams). Blood samples for measurement of plasma glucose and insulin levels will be drawn every 30 minutes for 120 minutes. Insulin sensitivity (IS) will be calculated using the Matsuda Index (IS = $10,000/\sqrt{[\text{fasting glucose} \times \text{fasting insulin}] \times [\text{mean glucose} \times \text{mean insulin}]}$)⁸¹ while insulin secretion (SEC) will be calculated as the change in insulin divided by the change in glucose from 0 to 30 min (SEC = $\Delta I_{0-30}/\Delta G_{0-30}$).⁸² DI will be calculated by multiplying both these values (DI = IS x SEC).⁸² Disposition index is an important predictor of future type 2 diabetes.⁸³

Subject Incentives: Subjects will be compensated \$100 for participation in the Study Visit.

Laboratory: Genomic DNA will be prepared from peripheral blood mononuclear cells and used for assessment of C3 genetic polymorphisms, gene copy-number variations of total C4, C4A, C4B, long genes and short genes. Cell bound levels of processed activation products C4d and C3d deposited on red blood cells will be determined by flow cytometry. B-lymphoblastoid cell lines for each subject enrolled in this study will be created to facilitate future molecular biologic and genetic studies.

Complement phenotypes: Protein levels for complement C3 and C4 from EDTA-plasma will be determined by single radial immunodiffusion (RID) assays using commercial kits from the Binding Sites (UK). Fast and Slow protein variants of complement C3, acidic C4A and basic C4B allotypes of complement C4 will be elucidated by immunofixation of EDTA-plasma resolved by high voltage agarose gel electrophoresis, and scanned by densitometer to quantify the relative expression levels of polymorphic variants.⁷⁴ C3a-desArg will be assayed by enzyme-linked immunosorbent assays (ELSA) using EDTA-plasma and commercial kits (BD Bioscience). Cell-bound levels of processed complement activation products on erythrocytes, E-3d and E-C4d, will be assayed by flow cytometry using specific monoclonal antibodies against C3d and C4d, respectively (Quidel).⁸⁴

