Sample size: Based on data from our previous study with 100 nonHispanic white subjects and 100 African-American subjects we have power 0.8 to detect a 15% racial difference in C4 levels and 7.5% difference in C3 levels.

Interpretation: There are two major portions of this aim. The first is to determine whether there are complement levels differences between the racial groups and the second is to determine how these affect previously demonstrated racial differences in cardiovascular risk¹². The former will be easily determined by comparing complement levels in the two groups. The hypothesis that these racial differences are responsible for at least some of the cardiometabolic racial differences will be proven if when complement levels are included in the regression equation they retain significance but the racial differences are lost. Lastly, even if racial differences in complement are not found or do not account for cardiometabolic risk differences it will still be important for us to determine whether the significant effects of complement described above in nonHispanic whites are present in African-American adolescents.

Specific Aim 2: To determine whether specific C3 polymorphisms, F versus S, A>G at rs11569562 and/or rs2250656, are associated with increased cardiometabolic risk in African-Americans.

Statistical Methods: As indicated above, the C3F gene has been associated with increased risk of myocardial infarction in several populations³⁶⁻³⁸ and Phillips et al⁴⁰ reported increased cardiometabolic risk in subjects with either an A/A or A/G versus subjects with a G/G genotype for both the rs11569562 and the rs2250656 sites. For rs11569562 in a European population ~ 25% of subjects had G/G and for rs2250656 ~10% had G/G. Frequencies in the African-American population are unknown. Data will be assessed for normality using the Shapiro Wilk test ($p>0.05$ indicative of normality). Non normal data will be log normalized if possible. Unpaired t-tests with unequal sample sizes will be used for comparisons for each of the measured normal variables between subjects with at least one A allele gene and those with two G alleles assuming the data is normally distributed. Mann-Whitney U tests will be used to assess non-normal data.

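### In Aim 1 race is fully aliased with study, so any between-study shift in the C3/C4 assay would enter the racial contrast in full, and the plan has no step to detect it or allow for it

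*Combined protocol and SAP*

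**What the plan says.** Under Research Design and Methods, Subjects, the plan is explicit: "we plan to recruit only African-American subjects". The white comparison group is supplied from elsewhere. Data analysis, Specific Aim 1, Statistical methods: "Complement levels from African-Americans in this proposal will be compared to those from nonHispanic whites in our current study". The only comparability claimed for the two studies is "Eligibility criteria are identical for both studies except for race".

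On measurement, Complement phenotypes says that C3 and C4 protein levels in EDTA-plasma "will be determined by single radial immunodiffusion (RID) assays using commercial kits". No assay CV is given for C3 or C4; the only measurement CVs in the document are for forearm blood flow. I found no mention of kit lots, shared runs, bridging samples, re-assay of white samples, or a study or batch term.

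On analysis, "Unpaired t-tests will be used to compare differences in C3 and C4 levels", and for covariates "We anticipate age and BMI differences will be minimal but should racial differences be found analysis of covariance will be done". Sample size for Aim 1 gives power 0.8 with 100 subjects per group for a 7.5% difference in C3 and a 15% difference in C4. On whether levels differ by race, the Interpretation paragraph says "The former will be easily determined by comparing complement levels in the two groups".

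**The concern.** A difference between the two groups is a difference between two studies. If the assay read even slightly higher or lower in one of them, that offset would be reported as a racial difference, or would hide a real one. The racial difference in C3 and C4 is the first half of Aim 1, and it feeds two further readings:

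- The second half of Aim 1 counts complement as explaining racial differences in risk if the race term loses significance once complement enters the regression. That race term also depends on the calibration of complement between studies.
- The Limitations section would read a racial difference in levels without a difference in complement genetics as pointing to lifestyle. An assay shift would produce the same pattern, because it moves protein levels and leaves genotypes alone. The section does not mention this explanation.

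**Working it through.** **1. Can race and study be separated?** Code 100 African-American subjects as race = 1, study = 1 and 100 white subjects as race = 0, study = 0. The design matrix with intercept, race and study has rank 2 of 3, so the two effects cannot be estimated separately, whatever covariates are added. If the assay in this study reads s% higher, the expected race contrast is (true difference + s).

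**2. What precision does the plan imply?** The documents give no mean, SD or CV for C3 or C4, so the stated power cannot be reproduced independently. It can be inverted. Inputs: 100 per group, power 0.80, differences of 7.5% (C3) and 15% (C4), all from the Aim 1 sample-size text. Two-sided alpha 0.05 is my assumption; 0.05 is stated only for Aims 2 and 3, and sidedness is not stated.

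- Detectable standardised difference for a two-sample t-test: d = 0.398.
- Implied between-subject CV = difference / d: C3 7.5/0.398 = 18.8%; C4 15/0.398 = 37.7%.
- SE of the contrast = CV × √(2/100): C3 18.8 × 0.1414 = 2.66%; C4 37.7 × 0.1414 = 5.33%.
- Smallest observed difference that reaches significance = 1.972 × SE: C3 5.25%; C4 10.5%.

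**3. Effect of a shift when there is no true difference.** This is the noncentral-t rejection probability with noncentrality s/SE. Shift sizes are assumptions, because the documents give no between-lot figure.

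| Assumed shift | C3 significant | C4 significant |
|---|---|---|
| 0% | 5% | 5% |
| 1% | 7% | 5% |
| 3% | 20% | 9% |
| 5% | 46% | 15% |
| 7.5% | 80% | 29% |
| 10% | 96% | 46% |

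**4. Effect of a shift opposing a true difference.** A 5% shift against a true 7.5% C3 difference leaves an expected contrast of 2.5%, and power falls from 0.80 to 0.15. Against a true 15% C4 difference it leaves 10%, and power falls to 0.46.

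**5. Does the planned covariance adjustment help?** I simulated C3 with BMI explaining 32% of its variance (assumed) and groups balanced on age and BMI. A 5% shift gave a mean adjusted race effect of about 5.0% and significance in 61% of runs. The bias is untouched, and rejection rises because the residual variance is smaller.

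**6. Does it carry into the regression that includes complement?** In a linear model with outcome = a + b·race + c·complement, adding s to complement in one race changes the fitted race coefficient from b to b − c·s. The rule based on losing the race effect is therefore exposed to the same shift.

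**The case against.** The strongest reply is that nothing in the documents shows a misalignment of assay runs. The white cohort is called the current study in one place and the previous study in another, and 75 white subjects are reported where the power statement uses 100. Some overlap in enrolment or assay runs cannot be excluded. That stands. A reader might infer that race, calendar period and assay run all coincide; only the coincidence of race and study is documented.

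Next, the shift sizes are assumed and treated as one constant offset. If either study used several lots, their shifts would partly average out, and at 1% the effect is close to nil. This also stands. A reader might infer that a modest shift could create or cancel the whole effect the study is powered for. By the plan's own figures, that would take about 7.5% for C3 and 15% for C4.

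Third, bridging has a price. With 20 re-assayed pairs and an assumed single-measurement CV of 5%, the SE of the ratio is 5% × √(2/20) = 1.58%. The C3 contrast SE becomes √(2.66² + 1.58²) = 3.10%, and power at 7.5% falls to about 0.68. At an assumed 10% CV it falls to about 0.44. For C4 at 15% the figures are about 0.77 and 0.68. Stored plasma may also have changed with age, which a re-assay ratio cannot tell apart from a lot change.

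Finally, the study is exploratory, and the plan says the within-race question matters whatever the race contrast shows. That limits the reach of the point but does not answer it. The plan still reads a between-study contrast as racial without any check.

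**Conclusion.** The point holds as a conditional one. Race and study are completely aliased in Aim 1, the plan does not address assay comparability, and nothing it proposes could remove a between-study shift. The documents do not show that such a shift exists, nor that different lots or runs were used.

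The exposure is greater for C3, where an assumed shift of 3% to 5% raises false significance from 5% to between 20% and 46%. For C4 a shift of 5% to 10% gives 15% to 46%. These figures rest on the plan's stated power, two-sided 0.05, 100 per group and a constant shift.

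The other between-race comparisons in Aim 1 share the aliasing. The within-race regressions and Aims 2 and 3, which use African-American subjects only, do not.

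**What to change.** - **If white-cohort EDTA-plasma aliquots remain:** re-assay a bridging set (for example 20) alongside the African-American samples on the same kit lots and estimate the between-study ratio. Report the race difference with and without that calibration, and carry the ratio's uncertainty into the confidence interval.
- **If none remain:** compare kit control or calibrator readings from the two studies, where they were kept.
- **In every case:** report the size of assay shift that would remove or create significance. On the implied SEs, an observed 7.5% C3 difference would lose significance if more than 7.5 − 5.25 = 2.25 points of it were shift; an observed 15% C4 difference, if more than 15 − 10.5 = 4.5 points were.
- **Wording:** in the Aim 1 Interpretation paragraph, replace "The former will be easily determined by comparing complement levels in the two groups" with a statement that the contrast is between studies and will be attributed to race only if it is robust to plausible assay shift. Apply the same caution to the rule for judging that complement explains the racial differences and to the lifestyle reading under Limitations.

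A rule that withholds attribution to race whenever the difference is no larger than the shift is not advised. After calibration it would count the shift twice, and it ignores the shift's sign and uncertainty.

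**Cost:** a few assays on stored plasma, whose availability the documents do not state, and a wider C3 interval (power at 7.5% of about 0.68 instead of 0.80 in the 20-pair, 5% CV example). If no bridging material exists, the only cost is a more cautious conclusion. This is a cheap improvement and needs no new recruitment.
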